8.2.3.2. Adverse events

All adverse events

Adverse events will be summarized by SOC and PT in terms of number and proportion of patients.

• Serious and non-serious adverse events

SAEs will be summarized by SOC and PT in terms of number and proportion of patients. Similarly, non-serious AEs will be summarized by SOC and PT in terms of number and proportion of patients.

• Safety specification

The following AEs included in the scope of the safety specification will be summarized in terms of number and its proportion of patients, as well as incidence and its 95% CI.

- Serious infections (including tuberculosis, pneumonia, pneumocystis pneumonia, sepsis, and opportunistic infection)
- Herpes zoster
- Neutrophils decreased, lymphocytes decreased, haemoglobin decreased
- Hepatic function disorder

- Hepatitis B virus reactivation (in patients with past history or complication of hepatitis B virus carrier)
- Gastrointestinal perforation
- Interstitial lung diseases
- Venous thromboembolism
- Malignancy
- Cardiovascular events (including lipids increased and hyperlipidaemia)
- Cardiovascular events (excluding lipids increased and hyperlipidaemia)
- Lipids increased and hyperlipidaemia
- Rhabdomyolysis and myopathy

In addition, patients who experienced AEs in the scope of the safety specification will be summarized in terms of n and proportion by SOC and PT, for different kinds of action taken and outcome.

• Timing of onset of elements in the safety specification

Patients who experienced AEs of each element in the safety specification will be summarized by timing of first onset, in terms of n and proportion as well as incidence and its 95% CI. For the purpose of summarization by time to onset, the denominator to calculate the proportion will be the number of patients who took at least one dose during each time category, and the denominator to calculate the incidence will be the duration of exposure in each time category. The categories for onset timing will be given by [\leq 15 weeks, >15 to \leq 30 weeks, >30 to \leq 45 weeks, >45 to \leq 60 weeks], except for malignancy, for which given by [\leq 15 weeks, >15 to \leq 30 weeks, >30 to \leq 45 weeks, >45 to \leq 60 weeks, >60 to \leq 75 weeks, >75 to \leq 90 weeks, >90 to \leq 105 weeks, >105 to \leq 120 weeks, >120 to \leq 135 weeks].

• Relationship between concomitant drugs and adverse events

To investigate the relationship between concomitant biologics/immunosuppressants or concomitant CYP3A4 inhibitors/CYP2C19 inhibitors and AEs included in the scope of the safety specification, development of those AEs will be summarized in patients with and without concomitant use of a biologic/immunosuppressant and in patients with and without concomitant use of a CYP3A4 inhibitor/CYP2C19 inhibitor, by PT in terms of number of patients. Concomitant drugs used after the first onset of a target event will be excluded from the summarization. Concomitant drugs considered in this investigation include:

- Biologics (including recombinants)/immunosuppressants: abatacept, adalimumab, anakinra, azathioprine, baminercept, canakinumab, certolizumab, certolizumab pegol, cyclosporine, efalizumab, etanercept, golimumab, infliximab, ofatumumab, rituximab, Syk kinase inhibitors, tacrolimus hydrate, tocilizumab, sarilumab, zanolimumab, vedolizumab, ustekinumab, secukinumab, ixekizumab, and 6-mercaptopurine
- CYP3A4 inhibitors/CYP2C19 inhibitors: clarithromycin, telithromycin, nefazodone, itraconazole, ketoconazole, atazanavir, darunavir, indinavir, lopinavir, nelfinavir, ritonavir, saquinavir, tipranavir, tacrolimus hydrate, cyclosporine, amitriptyline, clomipramine, fluconazole, fluvoxamine, imipramine, ticlopidine, esomeprazole, fluoxetine, moclobemide, omeprazole, and voriconazole

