7.2.3. Planned investigation period

The planned period covered by this study is as follows.

• Investigation period: May 2018 to June 2021

• Registration period: May 2018 to until the approval conditions for all cases investigations are lifted

However, when PMDA has accepted to continuing registration only, it is not necessary to enter new CRF.

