8.1.5. Analyses of time-to-event data

Kaplan-Meier plots will be presented for time-to-event data. Event-free patients will be censored at the end of their observation period or 60 weeks after the start of treatment, whichever came first. If the time to event exceeds 60 weeks, the patient will be treated as event-free and censored at 60 weeks. For malignancy, however, no such upper limit will be set for the time to onset, and malignancy-free patients will be censored at the end of their observation period.

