 - Duration of treatment >45 to ≤ 60 weeks
 - Duration of treatment >60 to ≤ 75 weeks
 - Duration of treatment >75 to ≤90 weeks

• Duration of treatment >90 to <105 weeks

- Duration of treatment >105 to <120 weeks
- Duration of treatment >120 to ≤135 weeks
- Duration of treatment >135 weeks

The duration of treatment is defined as the period from the start date of the treatment with this drug to the last observed administration date of this drug, including non-dosing days.

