8.2.3.1. Adverse reactions

• All adverse reactions

Adverse reactions will be summarized by SOC and PT in terms of number and proportion of patients.

Serious adverse reactions

Serious adverse reactions will be summarized by SOC and PT in terms of number and proportion of patients.

• Details of adverse reactions

Adverse reactions in different categories defined with respect to the following factors will be summarized by SOC and PT in terms of number and proportion of patients. For the factor time to onset, the number of patients who took at least one dose during each time category will be used as the denominator to calculate the proportion.

- Seriousness [serious, non-serious]
- Known/unknown [known, unknown]
- Time to onset [≤15 weeks, >15 to ≤30 weeks, >30 to ≤45 weeks, >45 to ≤60 weeks, >60 to ≤75 weeks, >75 to ≤90 weeks, >90 to ≤105 weeks, >105 to ≤120 weeks, >120 to ≤135 weeks, >135 weeks]
- Action taken [permanent discontinuation of treatment, temporary discontinuation or dose reduction, dose increase, no change]
- Outcome [not recovered, resolved/recovered, recovered with sequelae, improved, death, unknown]

Patients who experienced multiple adverse reactions of the same adverse reaction (identical PT) will be summarized as follows:

- For seriousness: Patients who experienced both serious and non-serious adverse reactions of the same PT will be handled as having experienced a serious event.
- For known/unknown: Priority will be given to "unknown" if both experienced.
- For time to onset: The day to the first onset will be used.
- For action taken: If multiple actions were taken, only one kind of action will be adopted with the order of priority being permanent discontinuation, temporary discontinuation/dose reduction, and other (no change or dose increase).
- For outcome: The outcome for the last event will be used.

Safety specification

The following adverse reactions included in the scope of the safety specification will be summarized in terms of number and proportion of patients, as well as incidence and its 95% CI.

- Serious infections (including tuberculosis, pneumonia, pneumocystis pneumonia, sepsis, and opportunistic infection)
- Herpes zoster
- Neutrophils decreased, lymphocytes decreased, haemoglobin decreased
- Hepatic function disorder
- Hepatitis B virus reactivation (in patients with past history or complication of hepatitis B virus carrier)
- Gastrointestinal perforation
- Interstitial lung diseases
- Venous thromboembolism

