- Malignancy
- Cardiovascular events (including lipids increased and hyperlipidaemia)
- Cardiovascular events (excluding lipids increased and hyperlipidaemia)
- Lipids increased and hyperlipidaemia
- Rhabdomyolysis and myopathy

In addition, patients who experienced adverse reactions in the scope of the safety specification will be summarized in terms of n and proportion by SOC and PT, for different kinds of action taken and outcome.

Timing of onset of elements in the safety specification

Patients who experienced adverse reactions of each element in the safety specification will be summarized by timing of first onset, in terms of n and proportion as well as incidence and its 95% CI. For the purpose of summarization by time to onset, the denominator to calculate the proportion will be the number of patients who took at least one dose during each time category, and the denominator to calculate the incidence will be the duration of exposure in each time category. The categories for onset timing will be given by $[\le 15 \text{ weeks}, > 15 \text{ to} \le 30 \text{ weeks}, > 30 \text{ to} \le 45 \text{ weeks}, > 45 \text{ to} \le 60 \text{ weeks}]$, except for malignancy, for which given by ≤ 15 weeks, ≥ 15 to ≤ 30 weeks, ≥ 30 to ≤ 45 weeks, ≥ 45 to ≤ 60 weeks, ≥ 60 to ≤ 75 weeks, >75 to ≤ 90 weeks, >90 to ≤ 105 weeks, >105 to ≤ 120 weeks, >120 to ≤ 135 weeks, >135 weeks].

Relationship between concomitant drugs and adverse reactions

To investigate the relationship between concomitant biologics/immunosuppressants or concomitant CYP3A4 inhibitors/CYP2C19 inhibitors and adverse reactions included in the scope of the safety specification, development of those adverse reactions will be summarized in patients with and without concomitant use of a biologic/immunosuppressant and in patients with and without concomitant use of a CYP3A4 inhibitor/CYP2C19 inhibitor, by PT in terms of number of patients. Concomitant drugs used after the first onset of a target event will be excluded from the summarization. Concomitant drugs considered in this investigation include:

- Biologics (including recombinants)/immunosuppressants: abatacept, adalimumab, anakinra, azathioprine, baminercept, canakinumab, certolizumab, certolizumab pegol, cyclosporine, efalizumab, etanercept, golimumab, infliximab, ofatumumab, rituximab, Syk kinase inhibitors, tacrolimus hydrate, tocilizumab, sarilumab, zanolimumab, vedolizumab, ustekinumab, secukinumab, ixekizumab, and 6-mercaptopurine

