8.2.3.3. Subgroup analyses

Analyses by dosage subgroup

(1) Safety analysis of the treatment with 10 mg BID

To evaluate the safety of the treatment with this drug administered mainly at a dose of 10 mg BID, the following analyses will be performed in the patients treated mainly at 10 mg BID defined in Section 5.4.1 and results will be compared with those in the entire SAS. To eliminate the effect of including patients who discontinued treatment during the induction phase, similar analyses will also be performed in patients treated mainly at 10 mg BID for a long term and results will be compared with those in the patients treated for a long term defined in Section 5.4.1:

- Adverse reactions of each element in the safety specification will be summarized in terms of number and proportion of patients as well as incidence and its 95% CI.
- Adverse reactions will be summarized by SOC and PT in terms of number and proportion of patients.

In addition, to investigate the temporal change in the risk of occurrence of each event, the following analyses will be performed in the patients treated mainly at 10 mg BID and results will be compared with those in the SAS:

- Patients who experienced adverse reactions of each element in the safety specification will be summarized by timing of first onset, in terms of n and proportion as well as incidence and its 95% CI. For the purpose of summarization by time to onset, the denominator to calculate the proportion will be the number of patients who took at least one dose during each time category, and the denominator to calculate the incidence will be the duration of exposure in each time category. The categories for onset timing will be given by [\leq 15 weeks, >15 to \leq 30 weeks, >30 to \leq 45 weeks, >45 to \leq 60 weeks], except for malignancy, for which given by [\leq 15 weeks, >15 to \leq 30 weeks, >30 to \leq 45 weeks, >45 to \leq 60 weeks, >60 to \leq 75 weeks, >75 to \leq 90 weeks, >90 to \leq 105 weeks, >105 to \leq 120 weeks, >120 to \leq 135 weeks, >135 weeks].
- A Kaplan-Meier plot will be presented for the time to first onset of each element in the safety specification.
- (2) Evaluation of dose response of the safety

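### SAP 8.2.3.2 ends the malignancy onset bands for all-causality adverse events at 135 weeks, while the parallel lists have a further >135 weeks band and follow-up can run to about 157–165 weeks

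*SAP*

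**What the plan says.** In SAP 8.2.3.2, under the timing of onset of safety-specification elements, patients with an adverse event are counted by band of first onset. Each band has a proportion (denominator: patients dosed in that band) and an incidence with 95% CI (denominator: exposure in that band). Most elements have four bands ending at Week 60. Malignancy has its own list ("weeks], except for malignancy, for which given by") of nine bands, the last being ">120 to \leq 135 weeks", after which the bracket closes.

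The parallel lists go one band further:
- SAP 8.2.3.1, time to onset in the details of adverse reactions: ">120 to ≤135 weeks, >135 weeks".
- SAP 8.2.3.1, timing of onset for malignancy: "135 weeks, >135 weeks".
- SAP 8.2.3.3, patients treated mainly at 10 mg BID: ">120 to \leq 135 weeks, >135 weeks". The dose-response analysis in the same section refers back to this list.
- SAP 8.2.2, dosing status: "Duration of treatment >135 weeks".

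Malignancy is exempt from the 60-week cap in SAP 6.1, 8.1.4, 8.1.5 and 8.2.3. For time-to-event data, "malignancy-free patients will be censored at the end of their observation period". Protocol 7.2.3 sets the calendar limits: "Investigation period: May 2018 to June 2021".

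**The concern.** The bands in a timing table should cover all the follow-up over which the event is counted. Here they do not. A malignancy first seen after Week 135 has no row, and the person-time after Week 135 enters no denominator. The SAP does not say whether such an event is to be dropped, placed in the last band, or given a band of its own.

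Two reconciliations are at stake. First, the bands may not sum to the malignancy total that 8.2.3.2 itself reports under the safety specification. Second, SAP 6.1 defines adverse reactions as the adverse events judged treatment-related, so they are a subset. A treatment-related malignancy after Week 135 would nevertheless have a row in the adverse-reaction timing table and none in the adverse-event one. A malignancy after Week 135 judged unrelated would have no row in either table. The SAP classes malignancy as an important identified risk, and it is the only element analysed beyond Week 60.

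**Working it through.** The documents give no maximum follow-up in weeks, so there is no stated figure to reproduce. The check is calendar arithmetic.

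**Inputs**
- Start: May 2018, day not given (Protocol 7.2.3). Range taken: 1 to 31 May 2018.
- End: June 2021, day not given (Protocol 7.2.3; SAP 2.1). A footnote in Protocol 7.2.5 defines the end as the last observation before June 2021, which read strictly is 31 May 2021. Range taken: 31 May to 30 June 2021.
- Upper edge of the last malignancy band in SAP 8.2.3.2: 135 weeks = 135 × 7 = 945 days.

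**Formulas**
- Maximum follow-up (weeks) = (end date − start date) / 7.
- Unbanded time = maximum follow-up − 135.
- Share = unbanded time / maximum follow-up.

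| Start | End | Days | Maximum (weeks) | Beyond 135 (weeks) | Share |
|---|---|---|---|---|---|
| 31 May 2018 | 31 May 2021 | 1096 | 156.6 | 21.6 | 13.8% |
| 1 May 2018 | 31 May 2021 | 1126 | 160.9 | 25.9 | 16.1% |
| 31 May 2018 | 30 June 2021 | 1126 | 160.9 | 25.9 | 16.1% |
| 1 May 2018 | 30 June 2021 | 1156 | 165.1 | 30.1 | 18.2% |

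Every combination passes 135 weeks.

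**Who can be affected.** The latest start that allows follow-up beyond 135 weeks is the end date minus 946 days:
- End 31 May 2021: 28 October 2018.
- End 30 June 2021: 27 November 2018.

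An early start is not enough. Protocol 7.2.5 and SAP 2.1 collect data only until discontinuation, so the patient must also still be on treatment past Week 135. The documents give no accrual or persistence figures, so this number cannot be computed.

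**Where a malignancy after Week 135 still appears**

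| Output | Included? |
|---|---|
| Overall malignancy n, proportion, incidence and CI for adverse events (8.2.3.2, using 8.1.4) | Yes |
| Kaplan-Meier rule for malignancy (8.1.5) | Yes, no cap |
| Listings (8.2.3, 9) | Yes |
| Adverse-reaction timing table (8.2.3.1), if judged related | Yes, >135 weeks |
| Adverse-event timing table (8.2.3.2) | No band |

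**The case against.** The strongest reply is that this is a drafting slip whose intended reading is plain. The sentence in 8.2.3.2 repeats those in 8.2.3.1 and 8.2.3.3 almost word for word, less the last band. The SAP revision history shows no intention to band adverse events differently from adverse reactions, and 8.2.2 already expects treatment beyond 135 weeks. The English SAP is also a translation for which no back translation was required, so the Japanese original may be complete. All of this supports treating the point as editorial. It does not remove it: the bracket in 8.2.3.2 closes cleanly after the ninth band, and a table programmed from the text would be incomplete.

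The second reply is that little depends on the table. The primary safety items in Protocol 7.7.2.1 centre on adverse reactions, whose timing list has the open band. That stands, and it limits the weight of the point.

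A reader might infer more than the documents support:
- That late malignancies are lost from the analysis. They are not; the overall estimates and the listings include them.
- That everyone who started before late November 2018 is affected. Only those still on treatment past Week 135 are, and the cutoff may be a month earlier.
- That the adverse-event table will show fewer late malignancies than the adverse-reaction table. That needs a treatment-related malignancy after Week 135, and no expected number is given.
- That malignancy is the reason for following patients past Week 60. The documents do not say so. Adverse events leading to discontinuation, treatment records and pregnancy status are also collected after Week 60.

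**Conclusion.** The point holds as a minor inconsistency. As written, the malignancy bands in SAP 8.2.3.2 leave up to about 22–30 weeks of possible follow-up (about 14–18% of a maximum of about 157–165 weeks) without a row, in this one table. The range rests on an unknown day in May 2018 for the earliest start and on an end between 31 May and 30 June 2021. These are maxima for the earliest starters who stayed on treatment. How many patients, or malignancies, fall beyond Week 135 is not known from the documents and could be few or none. The consequence is a table that may not reconcile with its own total or with the adverse-reaction table; the malignancy estimates themselves are not biased by it.

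**What to change.** Add a final >135 weeks category to the malignancy onset bands in SAP 8.2.3.2, so that they match 8.2.3.1 and 8.2.3.3. Check the Japanese original at the same time: if it already has the band, only the translation needs correcting. If the tables have already been produced, confirm that the malignancy adverse-event bands sum to the overall malignancy count and total exposure. The cost is one category in one sentence and one table row; no new data are needed.

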8.2.3.3. Subgroup analyses

Analyses by dosage subgroup

(1) Safety analysis of the treatment with 10 mg BID

To evaluate the safety of the treatment with this drug administered mainly at a dose of 10 mg BID, the following analyses will be performed in the patients treated mainly at 10 mg BID defined in Section 5.4.1 and results will be compared with those in the entire SAS. To eliminate the effect of including patients who discontinued treatment during the induction phase, similar analyses will also be performed in patients treated mainly at 10 mg BID for a long term and results will be compared with those in the patients treated for a long term defined in Section 5.4.1:

- Adverse reactions of each element in the safety specification will be summarized in terms of number and proportion of patients as well as incidence and its 95% CI.
- Adverse reactions will be summarized by SOC and PT in terms of number and proportion of patients.

In addition, to investigate the temporal change in the risk of occurrence of each event, the following analyses will be performed in the patients treated mainly at 10 mg BID and results will be compared with those in the SAS:

- Patients who experienced adverse reactions of each element in the safety specification will be summarized by timing of first onset, in terms of n and proportion as well as incidence and its 95% CI. For the purpose of summarization by time to onset, the denominator to calculate the proportion will be the number of patients who took at least one dose during each time category, and the denominator to calculate the incidence will be the duration of exposure in each time category. The categories for onset timing will be given by [\leq 15 weeks, >15 to \leq 30 weeks, >30 to \leq 45 weeks, >45 to \leq 60 weeks], except for malignancy, for which given by [\leq 15 weeks, >15 to \leq 30 weeks, >30 to \leq 45 weeks, >45 to \leq 60 weeks, >60 to \leq 75 weeks, >75 to \leq 90 weeks, >90 to \leq 105 weeks, >105 to \leq 120 weeks, >120 to \leq 135 weeks, >135 weeks].
- A Kaplan-Meier plot will be presented for the time to first onset of each element in the safety specification.
- (2) Evaluation of dose response of the safety

To evaluate the dose-response relationship concerning the safety of the treatment with this drug, the following analyses will be performed in the patients treated at a higher dose level defined in Section 5.4.1 and in the patients treated at a lower dose level. To eliminate the effect of including patients who discontinued treatment during the induction phase, similar analyses will also be performed in patients treated at a higher dose level for a long term and in patients treated at a lower dose level for a long term:

• Adverse reactions of each element in the safety specification will be summarized in terms of number and proportion of patients as well as incidence and its 95% CI. In addition, the risk ratio and risk difference with their 95% CI will be presented for the patients treated at a higher dose level compared with those at a lower dose level.

• Adverse reactions will be summarized by SOC and PT in terms of number and proportion of patients.

In addition, to investigate the temporal change in the risk of the occurrence of each event, the following analyses will be performed in the patients treated at a higher dose level and patients treated at a lower dose level:

[figure not shown]
- Patients who experienced adverse reactions of each element in the safety specification will be summarized by timing of first onset, in terms of n and proportion as well as incidence and its 95% CI. As for the denominator to calculate the proportion, the denominator to calculate the incidence, and the categories used for onset timing, the corresponding descriptions in (1) should be followed.
- A Kaplan-Meier plot will be presented for the time to first onset of any adverse reaction included in each element in the safety specification.

• Subgroup analyses regarding patient characteristics

According to Section 8.1.3, the risk ratio based on the proportion of patients who experienced adverse reactions of each element in the safety specification will be determined and graphically presented for different subgroups regarding each of the patient factors defined in Section 8.2.2 in which events developed in ≥ 10 patients. Risk ratios will not be calculated for subgroups in which events developed in < 10 patients.

For each relevant subgroup defined in Section 5.4.2, patients who experienced adverse reactions will be summarized by SOC and PT in terms of n and proportion.

Adverse reactions that developed in patients with a contraindication to Xeljanz will be listed in tabular form. Patients with a contraindication to Xeljanz who experienced adverse reactions will be summarized by SOC and PT in terms of n and proportion, as necessary.

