5.4. Subgroups

5.4.1. Subgroups by dose level

The following subgroups will be defined depending on the mean daily dose to evaluate the safety of this drug and the dose response of the safety in patients treated mainly at 10 mg BID:

• Subgroups by mean daily dose (patients treated mainly at 10 mg BID, patients treated at a higher dose level, patients treated at a lower dose level)

Among the patients in the SAS, those who were treated at a mean daily dose of 17 mg or higher will be defined as patients treated mainly at 10 mg BID.

Among the patients in the SAS, those who were treated at a mean daily dose of 15 mg or higher will be defined as patients treated at a higher dose level; similarly, those who were treated at a mean daily dose of <15 mg will be defined as patients treated at a lower dose level.

The mean daily dose should be calculated as:

Mean daily dose = (Total dose administered during the treatment period) / (Total number of days in the treatment period including non-dosing days)

• Patients treated for a long term

Among the patients in the SAS, those with a duration of treatment of >16 weeks are defined as patients treated for a long term.

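### In SAP 8.2.3.3(1), patients treated mainly at 10 mg BID are compared with groups that contain them, so the contrast in that part is pulled towards no difference

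*SAP*

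**What the plan says.** **Index group.** SAP 5.4.1 draws it from inside the safety analysis set (SAS): "Among the patients in the SAS, those who were treated at a mean daily dose of 17 mg or higher" count as treated mainly at 10 mg BID. The same section sets up the long-term set: "those with a duration of treatment of >16 weeks are defined as patients treated for a long term".

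**Comparators in SAP 8.2.3.3(1).**
- Safety-specification summaries and SOC/PT tables, run in the index group "defined in Section 5.4.1 and results will be compared with those in the entire SAS".
- The same analyses in long-term patients: "results will be compared with those in the patients treated for a long term defined in Section 5.4.1".
- Onset timing and Kaplan-Meier plots: "performed in the patients treated mainly at 10 mg BID and results will be compared with those in the SAS". No long-term version of these is planned.

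The outputs are counts, proportions, incidences with 95% CI, and plots. Part (1) specifies no ratio, difference or test.

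**Part (2) of the same section** compares 15 mg or more with less than 15 mg, overall and in long-term patients. It gives risk ratios and risk differences with 95% CIs for each safety-specification element.

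**The split at 17 mg.** A category below 17 mg appears only in the dosing-status tables of SAP 8.2.2. No safety output is planned for those patients on their own.

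**The concern.** By the definition in 5.4.1, every patient in the index group is also in its comparator. This is a part set against its own whole. Events at 17 mg or more enter both columns, so the two columns move together, and the larger the index group, the more alike they look whatever the true difference.

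Part (1) is the SAP's named evaluation of safety at mainly 10 mg BID, and the SAP says that results will be compared. A reader will therefore set two estimates, two intervals and two curves side by side. Because these share patients, overlapping intervals or close curves cannot be read as evidence that the groups are alike.

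**Working it through.** The plan states no figure for this comparison, so there is none to reproduce. The check is whether the overlap must attenuate the contrast, and by how much.

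**Inputs**
- Index group within the SAS, at 17 mg or more: SAP 5.4.1.
- Comparators: SAP 8.2.3.3(1).
- f, the share of the comparator at 17 mg or more: not in the documents, assumed 20% to 70%. For proportions it is the share of patients; for incidences, the share of person-time.
- R, the true ratio of 17 mg or more to less than 17 mg: assumed 1.5, 2 and 3.

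**Step 1: formula.** Let the risk (or rate) below 17 mg be r, so that it is Rr in the index group. The comparator's risk is fRr + (1 − f)r. The ratio a reader would form is

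Rr / [fRr + (1 − f)r] = R / (fR + 1 − f).

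The difference a reader would form is Rr − [fRr + (1 − f)r] = (1 − f)(Rr − r), which is (1 − f) times the disjoint difference. For any f strictly between 0 and 1 and any R above 1, the ratio is closer to 1 and the difference closer to 0. The direction is certain; only the size depends on f and R.

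**Step 2: numbers.** For example, R = 2 and f = 0.5 gives 2 / (1 + 0.5) = 1.33.

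| f | R = 1.5 | R = 2 | R = 3 | Share of difference kept |
|---|---|---|---|---|
| 20% | 1.36 | 1.67 | 2.14 | 80% |
| 50% | 1.20 | 1.33 | 1.50 | 50% |
| 70% | 1.11 | 1.18 | 1.25 | 30% |

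Illustration with assumed risks of 16% and 8% and f = 50%: the SAS risk is 0.5 × 16% + 0.5 × 8% = 12%. The disjoint contrast is a ratio of 2.0 and a difference of 8 points. Against the entire SAS it is 16/12 = 1.33 and 4 points.

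**Step 3: does part (2) supply the missing contrast?** SAP 2.1 describes daily totals of 20 mg and 10 mg. For a patient only ever on those two levels, with a fraction q of days at 20 mg, the mean daily dose is 10 + 10q. A mean of 15 mg means q = 50%, and 17 mg means q = 70%. So the group at 15 mg or more includes patients with 50% to just under 70% of days at the higher level, whom 5.4.1 leaves out of the index group. Part (2) is disjoint, but at a different boundary.

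**Step 4: is the full-SAS contrast at 17 mg clean?** No. Take induction at 20 mg/day followed by 10 mg/day. After 8 weeks of induction, the mean falls to 17 mg when 20 × 8 + 10(t − 8) = 17t, so t = 80/7 = 11.4 weeks. After 16 weeks of induction, t = 160/7 = 22.9 weeks. Patients who stop before those times land in the index group because they stopped early. Restricting to more than 16 weeks removes this for 8-week induction. For 16-week induction, stops between 16 and 22.9 weeks still fall in the index group.

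**The case against.** The case against giving this much weight is substantial.

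- **Part (1) is descriptive.** It displays no ratio or test, and SAP 4.2 sets no decision rules. A reader might infer that the SAP will report an attenuated risk ratio, or treat overlapping intervals as showing no difference. It says neither. The ratios above are ones a reader would form. The incidence and interval within the index group itself are not diluted at all. This stands.
- **Part (2) makes a disjoint dose comparison** with ratios and differences, and every patient at 17 mg or more is in its higher-dose group. A reader might infer that any excess risk at 10 mg BID is masked throughout the plan. The documents do not support that; the dilution is confined to part (1). What remains is that patients from 15 to under 17 mg are pooled with the index group, in numbers the documents do not give.
- **Much can be recovered by subtraction.** Counts are additive, SAP 8.2.1 reports SAS numbers by mean daily dose, and person-time follows from the incidence formula in SAP 8.1.4. This stands for counts, proportions and incidences, although every interval would need recomputing. The Kaplan-Meier curve below 17 mg cannot be recovered from the plots.
- **The complement is not a clean control in the full SAS.** SAP 8.2.3.3 itself names discontinuation during induction as an effect to eliminate. Removing the overlap would show that artefact undiluted. This stands and shapes the fix.
- **Benchmarking a subgroup against the whole is a familiar display** in single-arm surveillance, and no primary analysis item changes. This is true, and it is a reason to keep the SAS column, not a reason to omit the complement.

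**Conclusion.** The point holds for part (1) of SAP 8.2.3.3. All its comparators contain the index patients, no safety output is planned for patients below 17 mg alone, and the contrast is therefore pulled towards no difference. A true ratio of 2 would read as about 1.67 to 1.18 for an index share of 20% to 70%, with 80% down to 30% of the difference kept. The direction follows from the definitions. The size rests on an assumed share and an assumed true ratio, so it may be modest or large.

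This is a gap in a descriptive comparison and does not make a reported estimate wrong. Part (2) mitigates it in part, without isolating the group for which part (1) was written. A contrast at 17 mg in the full SAS should not be taken as a clean measure of risk at 10 mg BID, because early discontinuation feeds the index group. The long-term comparison is the better reading, with the residual limit shown in step 4.

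**What to change.** In SAP 8.2.3.3(1):

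1. Add the complement, SAS patients with a mean daily dose below 17 mg, as the comparator for the safety-specification counts and incidences, SOC/PT tables, onset-timing tables and Kaplan-Meier plots. Keep the entire SAS as context.
2. Make the comparison within long-term patients (17 mg or more against less than 17 mg, both treated for more than 16 weeks) the main reading.
3. State that the full-SAS contrast at 17 mg is affected by patients who discontinued during induction. The onset-timing tables and Kaplan-Meier plots should carry the same note, since they are planned only for the full set.

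The cost is SAP wording plus one extra column and curve. The category below 17 mg already exists in SAP 8.2.2, and no new data are needed. The change concerns the analysis only and implies no view on dosing.
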